## Measures

### Subjective measures (Table 1):

The following measures comprise the TobPRAC Screening Questionnaire (developed as part of an NCI contract; N01-PC-64402):

- 1) Tobacco Use History and Exposure, derived from the Tobacco Use Supplement to the 2010 Current Population Survey and Population Assessment of Tobacco and Health (PATH) Survey, measures variables such as smoking amount, cigarette brand, age of initiation of smoking, number of quit attempts, duration of quit attempts, duration of smoking;
- 2) Demographic History inquires about age and gender, race, ethnicity, current occupation and usual occupation, and income;

- 3) Medical History and Current Health Status lists current diagnoses, symptoms and past health problems;
- 4) Concomitant Medications Questionnaire lists medications that are currently being taken;
- 5) Prime MD is a brief questionnaire developed for evaluation of mental disorders by primary care physicians (35);
- 6) Centers for Epidemiological Studies 20-item scale (CES-D) assesses current symptoms of depression (36);
- 7) Short Michigan Alcohol Screening Test (SMAST) Short form assesses any negative consequences from alcohol use by self report (37); and
- 8) Drug Abuse Screening Test (DAST) assesses negative consequences from using drugs of abuse (38).

**TABLE 1 - SUBJECTIVE MEASURES**

	Screen	Sample	Baseline		Intervention						F -up	Phone f-ups	
WEEKS	-93	-92	-91	-00	1	2	3	4	6	8	20	12 & 32	
TobPRAC Screening Questionnaire													
Tobacco Use History and Exposure; Smoking Cessation	X												
Demographics	X												
Medical History & Current Health Status	X												
CES-D	X										X		
Prime MD	X										X		
MAST	X												
DAST	X												
Biomarker Modifier Questionnaires													
Environmental & Social Influences Questionnaire			X								X		X
NIAAA Alcohol Use Questionnaire			X								X		X
Drug Use Questionnaire			X								X		X
Perceived Stress Questionnaire			X			X					X		X
Health Changes Questionnaire		X	X	X	X	X			X	X	X	X	X
Respiratory symptoms Questionnaire				X		X			X	X	X		
Concomitant Medications	X	X	X	X	X	X			X	X	X	X	X
Other Subjective Measures													
Adverse Events		X	X	X	X	X	X	X	X	X	X	X	X
Tobacco Daily Diary (IVR)		X	X	X	X	X	X	X	X	X	X		
Daily Use Summary	X	X	X	X	X	X	X	X	X	X	X	X	X
Fagerstrom (FTND) Test for Nicotine Dependence	X				X	X			X		X		X
Wis. Index of Smoking Dependence Motives WISDM	X				X	X			X		X		
Stages of Change	X										X		X
Cigarette Evaluation Scale	X	X	X	X	X	X			X	X	X		X
Product Evaluation Scale	X	X			X	X			X	X	X		X
Drug Effects/Liking	X	X			X	X			X	X	X		
Perceived Health Risk	X	X			X	X			X		X		
Odor and Haptics	X	X							X				
Tobacco Purchase Task	X	X				X			X		X		
PANAS			X	X		X			X		X		
MN Withdrawal Scale			X	X	X	X			X	X	X		
Questionnaire of Smoking/Snus Urges			X	X	X	X			X		X		

10/17/2013

Interest in Switching/Quitting		X								X	X	
WEEKS	-93	-92	-91	-00	1	2	3	4	6	8	20	
Abbreviations: CESD= Centers for Epidemiological Studies-Depression, MAST=Michigan Alcohol Screening Test, DAST=Drug Abuse Screening Test;  Consumer Perception Measures from Project 3 including Oral/Haptic Scale.												

### *Biomarker Modifier Questionnaires*

The following measures comprise Biomarker Modifier Questionnaires (measures of factors that may moderate biomarkers of exposure and effect):

- 1) Environmental and Social Influences Questionnaire consists of questions related to tobacco smoke exposure at home, work and socially (40);
- 2) NIAAA Alcohol Use Questionnaire examines rate of alcohol use, current (last month) and lifetime. This questionnaire has been adapted to include lifetime maximum use patterns (41);
- 3) Recreational Drug Use History assesses amount, frequency and date of last use of recreational drugs;
- 4) Perceived Stress Questionnaire is a 14-item form measuring the degree to which life situations are appraised as stressful (43);
- 5) Health Changes Questionnaire assesses any new health problems since their last clinic visit;
- 6) Respiratory Symptoms Questionnaire is used to rate cough, phlegm production, shortness of breath and other respiratory symptoms on a scale ranging from 0 = none up to 10 = severe with a total respiratory score determined by adding the scores of each of these items.

### *Subjective outcome measures:*

- 1) Interactive Voice Response system will be used on a daily basis to record amount of product use, cigarette and other nicotine containing products and tobacco use status will be reviewed and recorded at each clinic visit;
- 2) Fagerstrom Test for Nicotine Dependence (FTND) (44);
- 3) Wisconsin Index of Smoking Dependence Motives is a multidimensional measure of dependence based on theoretically grounded motives for drug use and intended to reflect mechanisms underlying dependence and has been found to be related to smoking heaviness, DSM-IV symptoms of depression and relapse (45);
- 4) Minnesota Nicotine Withdrawal Scale (46);
- 5) Questionnaire of Smoking Urges, a 32-item questionnaire on smoking urges, assesses a multidimensional conceptualization of craving to smoke (47);
- 6) Adverse Events Scale assesses the nature, severity, duration, action taken, and outcome of adverse events related to tobacco product use;
- 7) Perceived Health Risks Assessment asks subjects to rate their perception of their usual tobacco product against the study product to which they were randomly assigned;
- 8) Product Evaluation Scale is a 7-point Likert-type scale that is modified from the Cigarette Evaluation Scale (48). In addition, items from a scale that was used to evaluate various medicinal nicotine products is incorporated in the Product Evaluation Scale (49). This scale has been used in a number of our studies. Cigarette Evaluation Scale will be used at baseline;
- 9) Drug Effects/Liking Questionnaire (50);
- 10) Stages of Change (51);
- 11) Consumer Product Perception. This measure will be developed by Project 3 of this U19 and include cognitive and affective measures and Odor/Haptics; and
- 12) Tobacco Purchase Task. Participants will be asked "How much would you be willing to pay for one tin of Camel Snus?" As a reference point, participants are also asked to report how

much they usually pay for one pack of cigarettes. The ratio of these prices can give an indication of the relative value of Camel Snus, and would allow comparison across the study sites, where cigarette prices vary. Subjects will also be provided the Tobacco Purchase Task developed, which will be used to generate demand curves by asking participants to report the number of units of a tobacco product that they would consume in a day if the units cost various amounts of money. This procedure has been used to study demand for cigarettes (52-53).

13) Interest in Switching or Quitting assesses interest in switching from cigarettes to the Camel Snus if it were not for the study; impact on interest in quitting tobacco use; and interest in paying for the product.

A panel of biomarkers has been selected to represent exposures to different toxicants and different disease risk factors. Samples will be analyzed for some or all of the following biomarkers and will be sent to a Biobank with de-identified information. Please see Table 2 for list of biomarkers.

1. Carcinogen biomarkers of exposure and effect and cardiovascular risk indicators were chosen because they have shown reasonable laboratory reproducibility, have clear differences in levels between smokers and nonsmokers and/or decrease upon tobacco cessation (33-34).
2. Cardiovascular biomarkers were selected because they are associated with different pathogenesis for disease and have also shown reasonable laboratory reproducibility.
3. Nicotine exposure and metabolite ratio (NMR) and the total nicotine equivalents will be determined. The latter accounts for 73-96% of the nicotine dose and are a useful measure of daily nicotine exposure. The NMR is an indicator of CYP2A6 enzyme activity and is the ratio between two nicotine metabolites, cotinine and trans-3'-hydroxycontinine (3-HC).

**TABLE 2 - BIOMARKER MEASURES**

Biomarkers for Carcinogen Exposure											
WEEKS	Screen	Sample	Baseline			Intervention					20 F-up 
	-93	-92	-91	-0	1	2	3	4	6	8	20
Total NNAL			X	X		X		X		X	
Total NNN			X	X		X		X		X	
Phenanthrene Tetroal			X	X		X		X		X	
Mercapturic acids of acrolein, benzene, 1,3-butadiene, crotonaldehyde, and ethylene oxide			X	X		X		X		X	
PGEM			X	X		X		X		X	
8-epi-PGF 2α			X	X		X		X		X	
Nicotine Exposure and Metabolite Ratio											
Total nicotine equivalents (Serum/Urine)			X	X				X		X	X
Nicotine metabolite ratio (serum)				X							
C-Reactive protein*				X				X		X	
Hematology				X				X		X	
Other Biomarkers											
Alveolar carbon monoxide (CO) 	X	X	X	X	X	X	X	X	X	X	
Oxygen saturation	X	X	X	X		X	X	X	X	X	

Expectorated SLT samples/Cig Butts and Filters				2X				X			
Vital signs and weight	X	X	X	X		X	X	X	X	X	X
Buccal cells				X				X		X	
Urine pregnancy screen	X										
Biobank Samples											
Urine			X	X		 X		 X	X	X	X
Spot urine (if appropriate)					X	X	X	X	X	X	X
Blood				X		X		X		X	X
Genetic analysis 											
WEEKS	-93	-92	-91	-0	1	2	3	4	6	8	20

Justification for Biomarkers in Core B and [name] et al., (2005); Cigarette butts only  
Samples collected at weeks 2 and 4 will be stored for potential analyses in the future as needed or funded.  
Only week 20 at follow-up will be a clinic visit, week 12 and 32 are telephone; Samples will be stored for future funding for analysis for genetic predisposition for tobacco toxicant metabolism, behavior and harm. Abbreviations: Total NNAL: 4-(Methylnitrosamino)-1-(3-pyridyl)-1-butanol and its glucuronides; Total NNN: N'-Nitrosornornicotine and its glucuronides; PheT: r-1,t-2,3,c-4-Tetrahydroxy-1,2,3,4-tetrahydrophenanthrene; Mercapturic acids: S-Phenylmercapturic acid; Monohydroxybutylmercapturic acid; 3-Hydroxypropylmercapturic acid; 4-Hydroxybut-2-ylmercapturic acid; 2-Hydroxyethylmercapturic acid; PGE-M: 11- $\alpha$ -Hydroxy-9,15-dioxo-2,3,4,5-tetranorprostane-1,20-dioic acid; 8-epi-PGF2 $\alpha$ ; 9,11,15-Trihydroxyprosta-5,13-dien-1-oic acid. NOTE: Minor tobacco alkaloids (nornicotine, anabasine, anatabine, myosamine and cotinine) will be analyzed in 50 complete substitution subjects for the analysis proposed by Project 1.

Other biomarkers will include:

1. Exhaled carbon monoxide (CO) and oxygen saturation as indicators of the extent to which red blood cells may be carrying their usual load of oxygen.
2. Biobank: Other tobacco-related biomarkers for assessment in blood, urine, or buccal cells may be determined to be necessary or may be developed over time and these additional assays will be completed as appropriate. Also, in the future, samples may be analyzed for genetic predisposition for tobacco toxicant metabolism, behavior and harm.

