### **Eligibility Criteria**

Subjects must meet the following criteria for eligibility:

The inclusion criteria are the following:

- a) Male or female subjects who are at least 18 years of age;
- b) Smoking history of  $\geq 10$  cigarettes daily and  $CO > 10$  ppm or if  $CO < 10$  ppm a NicAlert equal to 6 (over  $\sim 1000$  ng/mL cotinine concentration in urine). Subjects who smoke  $> 5$  to 9 cigarettes per day will be eligible, but their NicAlert level must be equal to 6;
- c) Smoking daily for at least 1 year and no serious quit attempts in the last 3 months (to ensure stability of daily smoking, particularly for those randomized to the continued smoking group);
- d) No unstable and significant medical or psychiatric conditions as determined by medical history and Prime-MD (to ensure safety of the subject, to minimize the effects of poor health on biomarker measures and to maximize compliance to study procedures);
- e) Lack of stabilization of medications (determined by study MD);
- f) Subject has provided written informed consent to participate in the study (adolescents under the age of 18 will be excluded because this project involves continued use of tobacco products and new tobacco products);

The exclusion criteria are the following:

- a) Immune system disorders, respiratory diseases, kidney or liver diseases or any other medical disorders that may affect biomarker data;
- b) Current or recent (<3 months) alcohol or drug abuse problems;
- c) Regular tobacco use (e.g., greater than weekly or 9 days in last 30 days) other than cigarettes;

- d) Use of smokeless tobacco products within the last 3 months;
- e) Use of roll your own cigarettes that are unfiltered or not machine rolled;
- f) Currently using nicotine replacement or other tobacco cessation products (to minimize confounding effects of another product) or intention to quit in next three months;
- g) Pregnant or breastfeeding (due to toxic effects from tobacco products).
- h) Unable to read for comprehension or completion of study documents.
- i) *Clinical Trial Additional Exclusion Criteria:* Regular substance use (other than alcohol) defined as use of a substance 15 of the last 30 days. This will be assessed via the Drug Use Questionnaire-1month.

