If subjects meet the eligibility criteria for the study, they will be asked to attend an orientation meeting where the entire study will be explained in detail, informed consent will be obtained and the Screening Questionnaires will be completed (Appendix A, Scales and Subjective Measures). Pregnancy exclusion will be confirmed through a urine test.

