### **6.4 Study Procedures**

#### ***Sampling Phase:***

The purpose of this phase will be to gauge product acceptance, reduce dropouts in the clinical trial and recruit subjects in the clinical trial that may be more representative of those who might purchase and use the product. Subjects will be provided the product for one week to determine palatability, sensory and consumer perception and initial pattern of product use. Subjects will return to the clinic after one week to determine their interest in continuing in the study.

During the orientation visit of this sampling phase, we will collect data that may influence the subject's perception of the product. These measures include basic demographic data and smoking history, consistent with questions used in the Tobacco Use Supplement to the 2010 Current Population Survey, and in the Population Assessment of Tobacco and Health (PATH) Survey allowing comparisons with a nationally representative sample of smokers. Additionally, we will use the Fagerstrom Test for Nicotine Dependence (FTND), Wisconsin Inventory of Smoking Dependence Motives (WISDM), Cigarette Evaluation Scale, Stages of Change scale PrimeMD, CES-D, Short Michigan Alcohol Screening Test (SMAST) and Drug Abuse Screening Test (DAST) and Perceived Health Risk of cigarettes. At the orientation visit, subjects will be instructed on how to use the product and presented with the Winterhill and Robust flavor snus tins. They will be instructed to smell the product and choose a flavor to try during the visit. After smelling the product, subjects will rate the sensory perception, taste and appeal of the product immediately after this initial exposure using the Odor/Haptic Scale (see Project 3). Afterward, the subject will place the snus pouch between their lip and gum for a 5 minute period and then expectorate the pouch. Subjects will complete the Product Evaluation Scale (PES), Drug Effects/Liking Questionnaire, Tobacco Purchase Task and Perceived Health Risk after expectorating the snus. Participants will then be provided Camel Snus to use at home (4 tins @ 15 pouches per tin) and told to "Use the product as you wish over the next week. If subjects want more, they can return to the clinic for a maximum of 14 tins/week. Camel Snus was

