#### ***Clinical Trial Phase:***

At the end of the sampling phase, eligibility for the clinical trial phase will be determined. Eligible subjects will have used an average of at least 2 sachets of Camel Snus daily during the sampling phase or at least 7 snus sachets used over most days during the sampling period. Subjects must be willing to attend clinic visits weekly for 4 weeks and biweekly visits for 6 weeks and a follow-up visit at 12 weeks post study product use and agree to be called at 4 and 24 weeks post-study. Subjects who wish to continue in the study will undergo 2 weeks of baseline where they will resume smoking and then will be randomized to one of five experimental conditions.

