#### **Experimental period:**

After the baseline assessment, subjects will be randomized to one of five experimental conditions: 1) smoking usual brand cigarette controls, who after 8-weeks will be offered Camel Snus and instructed for partial or complete substitution of cigarettes (subject's choice); 2) complete substitution (i.e., no smoking) and *ad libitum* use of snus; 3) complete substitution (i.e., no smoking) and specific instructions for snus use based on the number of cigarettes smoked per day (if 10-20 cigarettes, use 8 pouches per day snus, and if >20 cigarettes then 12

pouches per day – these amounts were derived from a clinical trials conducted by us and by [name] and associates [personal communication]). 4) partial substitution with *ad libitum* use of both snus and cigarettes; and 5) partial substitution with controlled use of snus (paralleling the instructions for complete substitution condition) and *ad libitum* smoking. All subjects will be instructed to use the snus pouch for at least 5 minutes and optimally 30 minutes per occasion; Snus, but not cigarettes, will be provided to subjects at the clinic visits.

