Smoking Usual Brand Condition. Subjects in this condition will undergo all the procedures as those subjects assigned to Camel Snus, except they will be told to smoke their usual brand of cigarettes and follow their normal patterns. At the end of the 8-week period, they will be offered the product for up to 8 weeks, with a choice of how they want to use the product. They will return to the clinic at 9, 10 and 12 weeks for assessment of use patterns (1, 2 and 4 weeks on the product). During this period, subjects will keep daily diaries via Interactive Voice Response (IVR). After 4 weeks of product use, they will come to the clinic whenever they want products for up to 8 weeks. At these clinic visits, their tobacco use patterns will be assessed via the Daily Use Summary and subjective forms. At the end of the 8 weeks (Week 16) of snus use, subjects will bring in a first morning void urine sample for analysis of tobacco exposure measures. Subjects will be paid \$50 for the Week 16 visit. Follow-up will occur as described below after the 8-week product access period (Weeks 20, 28 and 40). If subjects in the Usual Brand Condition do not choose to use the Camel Snus, they will follow the Follow-up schedule for the snus arms.

Follow-up. Follow-up clinic visit will occur for all subjects at week 20 (12 weeks after the end of the trial period). Tobacco use status (amount and type of tobacco product use) will be determined. CO will be obtained and a first morning urine and blood sample. These samples will be stored for cotinine assessment. Follow-up calls will occur at week 12 and 32 (4 and 24-weeks post-study) and tobacco use will be assessed. Those continuing to smoke or use Camel Snus will be strongly advised to quit and treatment resources will be provided.

Product Compliance Sessions. At each visit, subjects will be asked and counseled about their use of Camel Snus. The procedures for inquiry and counseling will be standardized. An intervention manual for each of the conditions will be developed.

- Complete Substitution Condition: Subjects will be asked about any concerns or obstacles associated with only using Camel Snus. If difficulties are encountered, then subjects will be asked about why they think they are experiencing difficulties (e.g., taste,

lack of satisfaction, withdrawal symptoms) and will be asked to problem solve how to deal with these difficulties so that they can meet the requirements of the protocol.

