## **6.5 Potential Risks of Study Participation:**

The potential risks for subjects are minimal. Subjects' medical history will be reviewed at orientation prior to entry into the study. Subjects will be under medical supervision throughout their participation in the study and adverse symptoms will be recorded at each clinic visit and monitored by the PIs and study medical personnel. We will also be available 24 hours a day for emergency calls.

The major side effects associated with Camel Snus are nausea, dizziness and lightheadedness, mouth sores, gastrointestinal distress, headache, hiccups, dry mouth and sore throat. Nicotine is toxic to the fetus and pregnant women are excluded from participation.

The oral tobacco product administered to subjects is currently marketed and sold over-the-counter. All subjects are current regular smokers and thereby exposed to nicotine and tobacco toxicants. Oral tobacco products may be linked with an increased risk for oral and pancreatic cancer, although compared to cigarettes, the risk is dramatically less. The reduction in risk is largely due to delivery of lower number and sometimes levels of tobacco toxicants from smokeless tobacco to the user simply because the tobacco is not burned, which yields thousands of combustion products. However, as this study will examine, some users may maintain their baseline smoking rate while using oral tobacco thereby may increase their exposure to nicotine and perhaps some tobacco related toxicants. We will minimize this risk by seeing the subjects on a weekly and then bi-weekly basis to assess increased tobacco use. In addition, all subjects will be strongly advised to quit all tobacco use at the end of the study and will be provided cessation materials.

There is also the chance of continued use of the products after the study has ended; however, cessation of all tobacco products will be recommended to the subjects. If at any time the subject wants to quit smoking or use of all tobacco products, this decision will be encouraged and supported. Subjects will be provided with a treatment manual and referral to different treatments.

Other risks include blood draws and a trained laboratory technician or a registered nurse will obtain blood samples. Otherwise, the physiological and subjective measures will be noninvasive and should present no psychological or medical risk to the subject.

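### Pregnancy is excluded because of fetal toxicity, but the only test is at screening: nominally 3 weeks before randomisation and about 10 to 11 weeks before controls are offered snus

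*Combined protocol and SAP*

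**What the plan says.** Exclusion criterion (g) in Section 6.2 reads "Pregnant or breastfeeding (due to toxic effects from tobacco products", and Section 6.5 repeats the reason: "Nicotine is toxic to the fetus and pregnant women are excluded from participation". The Eligibility Criteria text ties verification to the orientation meeting: "Pregnancy exclusion will be confirmed through a urine test". Table 2 agrees. Its "Urine pregnancy screen" row carries one mark, under Screen (-93), and none at the sampling, baseline, intervention or follow-up visits.

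Snus is then supplied at up to three points (Section 6.4):

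- **Orientation.** Subjects try a pouch and take tins home. The sampling phase lasts a week: "Subjects will be provided the product for one week to determine palatability".
- **Randomisation.** "Subjects who wish to continue in the study will undergo 2 weeks of baseline where they will resume smoking", and then "After the baseline assessment, subjects will be randomized to one of five experimental conditions". Four of the five conditions use snus for 8 weeks.
- **Week 8, usual-brand controls only.** "At the end of the 8-week period, they will be offered the product for up to 8 weeks", which runs to Week 16.

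Section 6.4 also says that eligibility for the clinical trial phase is determined at the end of sampling. Criterion (i) adds a substance-use exclusion that applies only to that phase.

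**The concern.** The protocol gives a specific safety reason for this exclusion but checks it once, before a gap in supply. Two later supply points, randomisation for the snus arms and week 8 for the controls, rely on that single result. A woman who conceives after screening, or too shortly before it for the test to detect, can be randomised and given snus without any further test.

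The re-check of eligibility after sampling makes the gap more noticeable. The protocol has a point at which entry to the trial phase is decided on fresh information, and it uses that point for snus uptake and substance use but not for pregnancy. What is at stake is subject safety and whether the exclusion is verified at randomisation. The primary endpoint and its analysis are not affected.

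**Working it through.** **1. Age of the test at each supply point.** The documents state no such interval, so there is no plan figure to reproduce. The phase lengths are from Section 6.4.

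| Supply point | Sum of phases | Age of test |
|---|---|---|
| Orientation, first supply | same visit | 0 weeks |
| Randomisation | 1 (sampling) + 2 (baseline) | 3 weeks |
| Controls offered snus | 3 + 8 | 11 weeks |
| End of control access (Week 16) | 3 + 16 | up to 19 weeks |

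These are nominal figures, and no visit windows are given. The Baseline smoking period text places visit 00 in Week -1. If randomisation takes place at that visit, before two full weeks have passed, the second and third figures fall by about a week, to roughly 2 and 10.

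**2. What happens between the test and those points.** Table 1 lists the Health Changes Questionnaire and concomitant medications at sampling, baseline and later visits. The questionnaire is a self-report of new health problems. Neither item is a pregnancy test.

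**3. Whether a sample is available.** Subjects bring first-void urine to visit 00 (Baseline smoking period) and again at week 8 (Procedures for clinic visits). No new sample or visit is needed at either point.

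**4. Rough size.** The documents give no sex split or conception rate. Assume 45% women, 70% of them able to conceive, and 2% to 8% conceptions per woman-year. The formula is subjects × 0.45 × 0.70 × rate × weeks/52.

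- All 690 subjects: 690 × 0.45 × 0.70 = 217 women at risk. Over 3 weeks: 217 × 0.02 × 3/52 = 0.25, and 217 × 0.08 × 3/52 = 1.0.
- Controls, 690/5 = 138: 138 × 0.45 × 0.70 = 43 women at risk. Over 11 weeks: 43 × 0.02 × 11/52 = 0.18, and about 0.74 at 8% (unrounded 43.47 × 0.08 × 11/52).

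The two ranges overlap for the controls' first 3 weeks and must not be added. The control range also assumes that nobody drops out and that every woman accepts the offer. The offer is optional and the sample-size text allows for drop-out, so that range is on the high side for these rates.

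**5. What a repeat test can find.** A urine test misses very recent conceptions. This applies at visit 00 as much as at screening. A repeat therefore moves the undetected window later without removing it. It can find conceptions that were too early to detect at screening, and it misses those too early to detect at visit 00.

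**The case against.** The best defence is that the documents are consistent with one another. Pregnancy excludes, one urine test confirms it, and that test is at the visit where snus is first handed out. How often to re-test is then a design choice. This stands in part. A reader might infer that the trial begins supplying snus to women it has not tested, or that the Section 6.5 statement is false. The documents do not support either reading. First exposure is covered by a same-visit test, and randomisation and week 8 are points of re-supply. The fair description is that the exclusion is confirmed at entry and not confirmed again.

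A second defence is background exposure. Every subject is a daily smoker, and the protocol describes toxicant levels from snus as lower than from cigarettes. A missed pregnancy would therefore not move from unexposed to exposed. This limits the added harm but does not remove it. The protocol excludes pregnant smokers all the same, Section 6.5 concedes that using both products may raise nicotine exposure, and two of the arms allow unrestricted smoking alongside snus.

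Third, there are partial safeguards: eligibility is determined after sampling, health changes are asked about, and staff review subjects weekly under medical supervision. They are real, but for pregnancy they depend on the subject knowing and saying so.

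A reader might also infer that controls who test positive at week 8 must be refused snus under criterion (g). The documents do not say whether an entry criterion governs supply to subjects already randomised. That is a clinical decision for the protocol to state.

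Finally, the consent pages and one passage were removed before review, and the visit checklists are not shown. They may contain pregnancy instructions, and this cannot be checked either way.

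**Conclusion.** The point holds as a low-cost safety improvement. The only scheduled pregnancy test is nominally 3 weeks old at randomisation (possibly about 2) and about 10 to 11 weeks old at the control arm's snus offer. These intervals rest on stated phase lengths with no gaps between phases.

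The expected count is of the order of one pregnancy or fewer: 0.25 to 1.0 across all arms before randomisation, and 0.18 to 0.74 among controls by week 8. Both ranges depend wholly on the assumed sex split, fertility and conception rates. They show scale only and are not estimates for this trial. The case for change rests on the protocol's own fetal-toxicity rationale and on the sample already being in hand, more than on the numbers.

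**What to change.** 1. **Visit 00.** Add a mark for the urine pregnancy screen in Table 2 at visit 00. Run it on the first-void urine already brought to that visit, and read it before the arm is assigned. Add a matching sentence to the Eligibility Criteria text, so that criterion (g) is verified at randomisation as well as at screening.
2. **Week-8 offer to controls.** Reconcile criterion (g), the orientation test, Table 2 and Section 6.5 with the Experimental period and Smoking Usual Brand Condition text. State whether criterion (g) governs that supply and, if so, how it is verified. First-void urine is also collected at week 8 if the investigators decide that a test is needed.

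The cost is one test strip per woman able to conceive at visit 00 (a second for such women in the control arm if week 8 is included), a small protocol and consent amendment through the IRB, and a written step for handling a positive result. No added visit or sample is required. Neither change affects the randomisation ratio, the endpoints or the analysis.
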